3.3. Other Objectives

4. INVESTIGATIONAL PLAN

4.1. Clinical Study Design

This is a randomized, double-blind, placebo-controlled, multicenter Phase 2 study of repeated s.c. doses of 320 mg MOR106 or placebo, administered concomitantly with TCS. On Day 1 a loading dose (LD) will be administered (2 x 320mg MOR106, or placebo).

Adult subjects with moderate to severe AD who are candidates for systemic therapy will be randomized 2:1 to receive MOR106 or placebo every other week via s.c. injections (on Days 1, 15, 29, and 43). The 8-week treatment period, finishing on Day 57, is followed by a 16-week follow-up period, finishing on Day 169. A total of 60 subjects (n=40 on MOR106 and n=20 on placebo) will be enrolled in this study.

The screening visit will take place 7 to 28 days before baseline visit on Day 1. From screening onwards, subjects will apply a bland emollient at least twice daily, for at least 7 days prior to the baseline visit (i.e. Day 1). Emollient use must continue at least twice daily throughout the study (once daily in areas of TCS application).

TCS will not be permitted within 7 days prior to the baseline (Day 1) visit.

From Day 1 onwards, all subjects will apply concomitant open-label, once daily treatment with a medium potency TCS product. Other topical medications, such as a lower potency TCS or topical calcineurin inhibitors (TCI), may be used in addition to treat AD lesions located on the face, flexural, and genital areas. Once control has been achieved (i.e. lesions have cleared or almost cleared), TCS or TCI application to areas from which lesions have cleared will be limited to 2 days every week, in an interval of 3 or 4 days, until the end of the treatment period. TCS or TCI use will be reviewed at every visit by the investigator.

During the 16-week follow-up period, topical treatment of residual active AD lesions may continue as needed at the investigator's discretion.

Eligible subjects will undergo baseline evaluations and randomization, receiving first investigational medicinal product (IMP) dosing on Day 1. Following the completion of the first IMP administration, subjects will remain on site for a minimum of 2 hours after the injections. After the second (i.e. Day 15) and subsequent administrations subjects will remain on site for a minimum of 1 hour after each injection.

[figure not shown]

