6.1. Timing of Assessments

ICF needs to be signed before any study procedure, including screening procedure, is carried out.

The study assessments will be undertaken at time points as specified in the Schedule of Activities in Section 6.10. A window of ± 1 day is allowed for Visit 4 and a window of ± 2 days is allowed for all visits from Visit Day 15 onwards (Day 15 included).

Visit dates are always calculated from Day 1 (unless subject discontinues early and attends ETD visit). If a subject has an ETD visit, the follow-up visits are performed 14, 28, 42, 56, 70, 84, 98 and 112 days after the ETD visit.

Subjects who are discontinued from treatment during the dosing period will perform Day 57/ETD visit (14 days after the last dose) as the last visit in the dosing period before entering the follow-up period.

Subjects reported outcomes (are to be completed on site by the subject preferably before any other study-related procedures is performed.

12-Lead ECGs, vital signs, and physical examinations are to be recorded before invasive procedures are performed.

Blood samples should be taken after all noninvasive procedures (including completion of questionnaires) have been finished.

During the treatment period, procedures and assessments are to be performed prior to administration of IMP, except where indicated. For predose assessments, those should be done within 3 hours predose.

The following collection time windows apply:

- 12-Lead ECGs: A window of ±15 minutes is allowed for the Day 1 and Day 43 postdose assessments.
- Blood sampling: For samples < 24h: +/- 10 min; 24h samples: +/- 1 hour; 48, 72 and 96h samples: +/- 2 hours.
- Urine sampling: predose (within 2 hours before IMP dosing).

Safety assessments should be repeated at other time points and additional assessments made if clinically indicated.

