1. INTRODUCTION

This is a Phase II study to assess safety, tolerability and pharmacokinetics/exposure of MOR106.

The statistical analysis described by this analysis plan will be composed by tables, listings and figures (TLFs) presented in the following analysis parts:

- General subject information.
- [REDACTED]
- Pharmacokinetics (PK).
- Immunogenicity (ADA).
- Pharmacodynamics (PD) ([REDACTED])
- Safety (adverse events, laboratory, electrocardiogram (ECG), vital signs and physical examination sections).

As a consequence of early termination of the development of MOR106 in atopic dermatitis for futility at the time point of MOR106-CL-201 interim analysis, this SAP constitutes an accordingly adapted version in terms of statistical evaluations of efficacy and pharmacodynamics endpoints.

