2.3. STUDY ENDPOINTS

2.3.1. Primary Endpoints

The primary endpoints are the incidence and severity of treatment-emergent adverse events (TEAEs), serious adverse events (SAEs), and adverse events of special interest (AESIs) through Day 169/early discontinuation (ED) visit.

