3.3. SAFETY AND IMMUNOGENICITY ANALYSIS SET

All randomized subjects who received at least one dose of investigational medicinal product (IMP). This population will be named safety analysis set in the TLFs.

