14.1.2. Definition of Treatment-emergent Adverse Events

All adverse events starting as of the point of administration of study drug (i.e. start date of dose administration for s.c. dosing) until the last contact of the subject are defined as treatment-emergent adverse events (TEAE).

All adverse events tables will only show TEAEs.

Adverse events starting before administration of study drug (not TEAEs) will only be listed.

If an AE starts before administration of study drug but worsens after then:

- Until the worsening, the AE will be considered as a non-TEAE;
- From the worsening, the AE will be considered as a TEAE.

But if an AE starts before administration of study drug and improves after the first dose, the AE will not be considered as a TEAE.

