14.1.7. Calculation of Percentages

The denominator for all percentages will be the total number of subjects in each treatment group within the analysis period.

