14.1.8. Tables

Analysis periods will be replaced by their respective treatment via the randomization list (i.e., an as-randomized allocation) in all tables and listings.

Table 14.3.1.1: Treatment-emergent adverse events: Summary table

Tabulation per treatment group of the incidence of subjects:

- With at least one treatment-emergent adverse event (TEAE);
- With at least one serious TEAE;
- With at least one ISR;
- With at least one skin related TEAE;
- With at least one ISR (Grade 3 or higher) or skin related TEAE;
- With at least one AE leading to death;
- With at least one mild TEAE as worst intensity per treatment;
- With at least one moderate TEAE as worst intensity per treatment;
- With at least one severe TEAE as worst intensity per treatment;
- With at least one life threatening TEAE as worst intensity per treatment;
- With at least one fatal TEAE as worst intensity per treatment;
- With at least one TEAE considered related to study drug;
- With at least one TEAE for which the study drug was temporarily stopped;
- With at least one TEAE for which the study drug was permanently stopped.

Population: safety analysis set.

Table 14.3.1.2: Treatment-emergent adverse events up to 30 days after last dose: Summary table

Same as [Table 14.3.1.1](#), but restricted to events that started after start of study medication and up to 30 days after last dose.

Population: safety analysis set.

Table 14.3.1.3: Treatment-emergent adverse events: Tabulation of all adverse events

Incidence of subjects tabulation per treatment group of TEAE classified per system organ class and preferred term.

Population: safety analysis set.

Table 14.3.1.4: Treatment-emergent adverse events up to 30 days after last dose: Tabulation of all adverse events

Same as [Table 14.3.1.3](#), but restricted to events that started after start of study medication and up to 30 days after last dose.

Population: safety analysis set.

Table 14.3.1.5: Treatment-emergent adverse events: Tabulation of all adverse events by preferred term

Incidence of subjects tabulation per treatment group of TEAE classified per preferred term.

Population: safety analysis set.

Table 14.3.1.6: Treatment-emergent adverse events up to 30 days after last dose: Tabulation of all adverse events by preferred term

Same as [Table 14.3.1.5](#), but restricted to events that started after start of study medication and up to 30 days after last dose.

Population: safety analysis set.

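### The primary adverse-event results are planned only as crude percentages, although subjects who stop early are followed for less than 169 days; follow-up time and a Day 169 cumulative incidence should stand beside them

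*SAP*

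**What the plan says.** **Endpoint and window.** SAP 2.3.1 defines the primary endpoints as the incidence and severity of TEAEs, SAEs and AESIs "through Day 169/early discontinuation (ED) visit". Under SAP 14.1.2 an event counts as treatment-emergent from first dosing to the subject's last contact, so the length of the window depends on the subject.

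**Table and denominator.** The entry for Table 14.3.1.1 in SAP 14.1.8 begins "Tabulation per treatment group of the incidence of subjects" and lists the categories, including any TEAE, serious TEAE, and the combined row that corresponds to AESI. SAP 14.1.7 sets the denominator: "The denominator for all percentages will be the total number of subjects in each treatment group within the analysis period". The population is the safety analysis set, which SAP 3.3 defines as everyone randomized and dosed at least once.

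**Follow-up.** Protocol 4.1 plans the same schedule for both arms: eight weeks of treatment, "followed by a 16-week follow-up period, finishing on Day 169". Protocol 6.1 departs from this for subjects with an early treatment discontinuation (ETD) visit: "the follow-up visits are performed 14, 28, 42, 56, 70, 84, 98 and 112 days after the ETD visit". That visit falls 14 days after the last dose. Under SAP 5.1, the last analysis period of a subject who leaves the study ends on the discontinuation date.

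**Early termination.** SAP 1 reports that development in atopic dermatitis was stopped for futility at the interim analysis of another study, and that "this SAP constitutes an accordingly adapted version in terms of statistical evaluations of efficacy and pharmacodynamics endpoints". The change list in SAP 8.2.1 also drops the primary analysis, the per-protocol set, the time-to-event analysis and the terminal half-life. Some items in that list are redacted. No readable item attributed to the termination alters the adverse-event analysis.

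**The concern.** A subject with no event who is last seen on Day 127, or earlier after leaving the study, enters the percentage exactly as an event-free subject seen on Day 169 does. The result is then read as incidence over the whole study, although part of the denominator was not observed for that long. Absolute incidence is the main product of this trial, because safety is the primary objective and SAP 14 makes its analysis descriptive.

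The comparison between arms could also be affected. Protocol 4.5.4 allows the investigator to stop treatment for worsening disease, which may happen more often on placebo. Figure 14.3.1.1 (SAP 14.1.9) ranks preferred terms by risk difference with 95% confidence intervals. Shorter observation on placebo would push those differences against MOR106.

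**Working it through.** **1. The plan's own figure.** Protocol 7.1 gives an 87% chance of at least one event among 40 MOR106 subjects at 5% incidence. 1 − 0.95^40 = 0.871, so the figure reproduces.

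**2. End of follow-up after early stopping** (Protocol 6.1). Last dose day + 14 + 112:

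- Day 1: 1 + 14 + 112 = Day 127
- Day 15: Day 141
- Day 29: Day 155
- Day 43: Day 169

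**3. Expected crude percentage.** Let I be the true incidence through Day 169. With a constant hazard, the incidence by day d is F(d) = 1 − (1 − I)^(d/169). If a share g is followed only to day d, and stopping is unrelated to event risk, the expected crude value is (1 − g)·I + g·F(d).

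The documents give neither g nor the hazard. For illustration I take g = 15%, the non-evaluable share implied by Protocol 7.1 (1 − 51/60), and place all of it after the first dose, the earliest point at which dosed subjects can stop.

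| True I | F(127) | Crude value | Shortfall (points) |
|---|---|---|---|
| 5% | 3.78% | 0.85 × 5 + 0.15 × 3.78 = 4.82% | 0.2 |
| 20% | 15.44% | 0.85 × 20 + 0.15 × 15.44 = 19.32% | 0.7 |
| 50% | 40.60% | 0.85 × 50 + 0.15 × 40.60 = 48.59% | 1.4 |

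The detection probability in step 1 changes little. With 6 of 40 subjects followed to Day 127 it is 1 − 0.95^34 × (1 − 0.0378)^6 = 0.861, against 0.871. If every event falls before the shortened end of follow-up, as may be the case for injection-site reactions, the shortfall is zero.

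**4. Contrast between arms with no drug effect.** Suppose 25% of placebo and 5% of MOR106 subjects stop early. The spurious difference is (0.25 − 0.05) × [I − F(d)].

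- All stop after one dose (Day 127): 0.20 × (50 − 40.6) = 1.9 points at I = 50%. The same formula gives 1.3 points at 30% and 2.1 at 70%.
- All stop after three doses (Day 155): 0.4 to 0.6 points over the same range of I.

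**5. Leaving the study altogether.** As a sensitivity case only, suppose observation ends on Day 57. At I = 20%, F(57) = 7.25%, and the crude value is 18.1%, 16.8% or 13.6% if 15%, 25% or 50% leave. No section of either document sets or reports such an exit.

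**6. Whether time at risk recovers the target.** In a simulation of 200,000 subjects (true incidence 20%, half censored on Day 57, constant hazard), the crude proportion was 13.7%. Events per person-time converted to 169 days gave 20.1%.

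**The case against.** **The crude proportion matches the endpoint as worded.** The endpoint runs to Day 169 or the early discontinuation visit, and TEAEs run to last contact. This stands: the table does not contradict the endpoint. It also means that the endpoint pools windows of different length, so follow-up must be shown for the figure to be interpretable.

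**Other outputs already cover this.** The companion tables limited to 30 days after the last dose fall within the scheduled follow-up of anyone who completes the ETD visits. That stands, but they are also crude, and their windows run only to Day 31 after one dose against Day 73 after four. Table 14.1.1.3 counts subjects per interval, the disposition table gives reasons for stopping, and SAP 9.8 gives treatment duration. None of these is linked to an adverse-event percentage.

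**Exits for worsening disease are partly counted already.** Protocol 9.1.1 allows worsening of the target disease to be an adverse event, so such a subject would often already have a TEAE. This weakens the differential argument for any TEAE. It does not help for AESIs, which exclude exacerbations of atopic dermatitis (Protocol 9.1.4). Such exits also strain the non-informative censoring that Kaplan-Meier needs.

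**The trial is small and descriptive.** With about 40 and 20 subjects, rates by preferred term would rest on very few events: 5% of 40 is 2 subjects. This stands, and it limits the request to the three primary items.

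**Conclusion.** The point holds as a minor one. The direction is known: in expectation, with any shortened follow-up and any later risk, the crude percentage lies below the Day 169 incidence. Under the ETD rule the shortfall is about 0.2, 0.7 and 1.4 points at 5%, 20% and 50% true incidence. This assumes a constant hazard, non-informative stopping, and 15% of subjects stopping after the first dose. The shortfall is near zero for events confined to dosing.

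Three stronger readings are tempting, and the documents do not support them.

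- *Termination of development cut follow-up short here.* SAP 1 places the futility decision in another study, and SAP 8.1.1 still reports once subjects reach Day 169 or discontinue earlier. The protocol permits the sponsor to end the study, but that is not a record that it did.
- *The SAP was adapted only for efficacy and pharmacodynamics.* SAP 8.2.1 shows other changes, and part of the list is redacted. All that can be said is that no visible termination-driven change concerns adverse events.
- *The arm difference is biased by several points.* With 25% against 5% leaving the study on Day 57 and I = 50%, the difference would be 0.20 × (50 − 20.85) = 5.8 points. That needs early study exit which the documents do not describe. Protocol 4.5.4 asks subjects who stop treatment to continue follow-up.

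The effect would be material only with substantial or unequal study exit, and the planned adverse-event tables would not show that.

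**What to change.** Keep the crude percentages. Beside Table 14.3.1.1, report follow-up time (first dose to last contact) by arm. For any TEAE, any SAE and any AESI, add the Kaplan-Meier cumulative incidence at Day 169 by arm, censoring at last contact. The exposure-adjusted rate per subject-year is an optional further line. Do not extend this to preferred terms, where events will be few.

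The cost is a few table lines. The dates are already collected: onset days under SAP 14.1.6 and last-contact dates under SAP 9.1. One rule has to be added, because SAP 14.1.6 sets the onset day to missing when the start date is incomplete. Kaplan-Meier assumes non-informative censoring and the rate assumes a roughly constant hazard; a footnote should say so.

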14.1.9. Figures

Figure 14.3.1.1: Treatment-emergent adverse events sorted by risk difference

Graphical presentation ordered by risk difference versus placebo, presenting for each preferred term on the left panel the proportion of subjects with at least one TEAE for the active and placebo group and in the right panel the treatment difference and its 95% CI. The 95% CI is to be calculated using the Miettinen-Nurminen method, available in the FREQ procedure of SAS 9.4.

Population: safety analysis set.

14.1.10. Listings

Listing 16.2.10.1: Treatment-emergent adverse events: Summary listing

Summary listing per treatment group and per subject showing the following:

- Treatment start/stop date(time);
- AE preferred term (flagging ISR of grade 3 or higher and skin related AEs);
- AE start and end date(time);
- AE onset day in study;

- AE number;
- AE duration;
- AE intensity (CTCAE version 5.0);
- AE seriousness;
- AE relatedness to study drug;
- AE action taken;
- AE outcome.

This listing will show all information for each TEAE record fitting in one line. Each change in seriousness/intensity/relationship/action taken will be displayed each time in another line with the AE start date of this change and the AE stop date of this change.

Population: safety analysis set.

Listing 16.2.10.2: Treatment-emergent adverse events: Full listing

Full listing per treatment group and per subject and per analysis period showing the following:

- Treatment start date(time);
- AE system organ class, preferred term, verbatim term;
- AE start and end date(time);
- AE onset day in study;
- AE number;
- AE duration;
- AE intensity (CTCAE version 5.0);
- AE seriousness;
- AESI category (ISR and skin related events);
- AE relatedness to study drug;
- AE outcome;
- AE action taken;
- Concomitant therapy started (yes/no) because of the AE (and the generic name of the medication).

Each change in seriousness/intensity/relationship/action taken will not be displayed but the worst case for each parameter will be provided.

Population: safety analysis set.

Listing 16.2.10.3: Treatment-emergent adverse events: Summary listing of the grade 3 or higher adverse events

Same as Listing 16.2.10.1, only showing grade 3 or higher TEAEs.

Population: safety analysis set.

Listing 16.2.10.4: Treatment-emergent adverse events: Full listing of the grade 3 or higher adverse events

Same as [Listing 16.2.10.2](#), only showing grade 3 or higher TEAEs.

Population: safety analysis set.

Listing 16.2.10.5: Adverse events: Full listing of the serious adverse events

Same as [Listing 16.2.10.2](#), only showing SAEs, whether treatment-emergent or not.

Population: safety analysis set.

Listing 16.2.10.6: Pre-treatment adverse events: Full listing

Same as [Listing 16.2.10.2](#), only showing the AE records reported in the screening period.

Population: safety analysis set.

Listing 16.2.10.7: Adverse events: Summary listing of the injection site reactions events

Same as [Listing 16.2.10.1](#), only showing ISR events.

Population: safety analysis set.

Listing 16.2.10.8: Adverse events: Full listing of the injection site reactions events

Full listing per treatment group, per subject and time point showing the following:

- Treatment start date(time);
- ISR start and end date(time);
- ISR system organ class and preferred term;
- ISR anatomical site;
- ISR grade;
- ISR action taken;
- Narrative;
- Photography taken (yes/no);
- Erythema grade and extent;
- Edema grade and extent;
- Induration extent;
- Tenderness VAS;
- Itching VAS.

Population: safety analysis set.

Listing 16.2.10.9: Adverse events: Summary listing of the skin related adverse events

Same as Listing [16.2.10.1](#), only showing skin related events.

Population: safety analysis set.

Listing 16.2.10.10: Adverse events: Full listing of the skin related adverse events

Full listing per treatment group, per subject showing the following:

- Treatment start date(time);
- AE start and end date(time);
- AE system organ class and preferred term;
- Photography taken (yes/no and the anatomical site of lesion);
- Skin swab (yes/no and the anatomical site of lesion);
- Biopsy (yes/no and the anatomical site of lesion);
- Additional blood sample for cytokine analysis (yes/no);
- Tests and results (for cytokine analysis);
- Description of results and final diagnosis.

Population: safety analysis set.

Listing 16.2.10.11: Adverse events: Full listing of adverse events with temporarily discontinued as action

Same as [Listing 16.2.10.2](#) only showing AEs, with action taken study drug temporarily discontinued, whether related to study drug or not.

Population: safety analysis set.

Listing 16.2.10.12: Adverse events: Full listing of adverse events with permanently discontinued as action

Same as [Listing 16.2.10.2](#) only showing AEs, with action taken study drug permanently discontinued, whether related to study drug or not.

Population: safety analysis set.

Listing 16.2.10.13: Adverse events: Coding information

Overview listing of all distinct MedDRA coding pathways for all AEs reported in this study and population, from AE reported term until AE system organ class, also showing the subjects associated to each distinct coding pathway.

Population: safety analysis set.

14.2. NON-DRUG RELATED THERAPIES

14.2.1. Coding of Reported Terms

All therapies are expected to be coded using the MedDRA coding dictionary (version 21.0 or higher).

14.2.2. Calculation of the Relative Days

For both the start and the end dates of the therapy records, their day relative to the day of the first study drug administration will be calculated as described in section 5.4 of this SAP (calculation of relative days).

The relative day for a missing start date will be set to missing.

The relative day for an incomplete start or end date will be set to missing.

The relative day for a missing end date will be calculated up to the subject's date of last contact in study, and will be printed as '>X days'.

